3.0 PARTICIPANT SELECTION

A rostered AMC investigator (CTEP-registered physician investigator or non-physician investigator) must document that each protocol participant meets all stated eligibility criteria. Participating sites must have documentation that each eligibility requirement is satisfied prior to participant enrollment. In compliance with CTEP policy, no exceptions to eligibility criteria will be granted under any circumstance.

NOTE: Institutions may use this section of the protocol as an eligibility checklist for source documentation if it has been reviewed, signed, and dated before registration/randomization by the study investigator. If used as source documentation, this checklist must be printed, the investigator must check each item to document their assessment that the participant meets each eligibility criterion, and the completed checklist must be maintained in the participant's chart.

Participant ID Number: AMC-115 - _____ - _____

Participant Initials (L, F, M [optional]): _____

NOTE: All questions regarding eligibility should be directed to the study chair.

3.1 Eligibility Criteria

_____ 3.1.1 Participant can understand and is willing to sign a written informed consent document.

_____ 3.1.2 HIV positive. Documentation of HIV-1 infection by means of any one of the following:

- Documentation of an HIV diagnosis in the medical record by a licensed health care provider;
- Documentation of receipt of antiretroviral therapy (ART) (i.e., at least two different medications that do not constitute a prescription for pre-exposure prophylaxis [PrEP]) by a licensed health care provider. Documentation may be a record of an ART prescription in the medical record, a written prescription in the name of the participant for ART, or pill bottles for ART with a label showing the participant's name;
- HIV-1 RNA detection by a licensed HIV-1 RNA assay demonstrating >1000 RNA copies/mL;
- Any licensed HIV screening antibody and/or HIV antibody/antigen combination assay confirmed by a second licensed HIV assay such as a HIV-1 Western blot confirmation or HIV rapid multispot antibody differentiation assay.

Note: The term "licensed" refers to a kit that has been certified or licensed by an oversight body within the participating country and validated internally (e.g., U.S. FDA).

WHO (World Health Organization) and CDC (Centers for Disease Control and Prevention) guidelines mandate that confirmation of the initial test result must use a test that is different from the one used for the initial assessment. A reactive initial

rapid test should be confirmed by either another type of rapid assay, or an E/CIA that is based on a different antigen preparation and/or different test principle (e.g., indirect versus competitive), a Western blot, or a plasma HIV-1 RNA viral load.

- _____ 3.1.3 Patient was diagnosed with or treated for cancer within the last 5 years. Participants will qualify under one of three categories:
- New, primary or recurrent diagnosis –Considering or currently receiving cancer treatment
 - Metastatic or locally advanced cancer – This includes cases for which there are no current definitive therapy options for cure (i.e., inoperable) but may be considered for non-standard / non-curative therapies.
 - Prior diagnosis (within 5 years), in remission – Not currently on cancer treatment other than ART or maintenance therapy.
- _____ 3.1.4 Age \geq 18 years.
- _____ 3.1.5 Participant presents to an AMC domestic clinical trial site for either clinical care or research.

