Comorbid Conditions	Hepatitis B and C co-infection, cardiovascular disease (y/n, type), psychiatric conditions (y/n, type), non-cancer pulmonary conditions (y/n, type), hepatic dysfunction, hematologic abnormalities, renal dysfunction, neurologic disorders, endocrine disorders (including thyroid disorders, and diabetes)
HIV Care	Current ART regimen, years of ART use, year of HIV diagnosis, history of opportunistic infections, recent HIV viral load and CD4+ T-cell count
Status of Cancer Diagnosis	New, primary or recurrent disease; current metastatic or locally advanced, inoperable cancer; history of malignancy diagnosed within 5 years / cancer currently in remission
Cancer Details	Cancer type, date cancer diagnosed, diagnosis methods (clinical, cytology, histology), pathology performed, date of pathology, staging, staging methods (clinical, radiographic, surgical), current ECOG Performance Status (PS), current laboratory (CBC) values, cancer treatment history (for metastatic tumors or disease in remission)
Cancer Treatment Plan	Planned treatment (e.g., chemotherapy versus radiation versus surgery versus antiretroviral therapy [ART] only versus best supportive care/watchful waiting), location of planned treatment, timeline of planned treatment (start date), if past diagnosis and treatment- end date, enrollment in clinical trial, and clinical trial details

Quality of Life/Survivorship	European Organization for Research and Treatment of Cancer Quality of Life Questionnaire (EORTC QLQ-C30: Global health status, physical functioning, role functioning, emotional functioning, cognitive functioning, social functioning, fatigue, nausea and vomiting, pain, dyspnea, insomnia, appetite loss, constipation, diarrhea, financial toxicity) and Supportive Care Needs Survey Short Form 34 (SCNS-SF34: psychological needs, health system and information needs, physical and daily living needs, patient care and support needs, sexuality needs)
------------------------------	---

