8.2 Enrollment Data Collection

Following informed consent, additional, identifiable data will be collected, including:

- 8.2.1 Patient characteristics: Date of birth, biological sex, gender identity, race, ethnicity, height and weight
- 8.2.2 Sociodemographic: Socioeconomic status (e.g., ZIP code, housing status [homeless y/n, categories for frequency of housing insecurity]), health insurance (insured/uninsured, type if insured)
- 8.2.3 Health behaviors: Tobacco use (type, exposure [pack/day, years use]), illicit drug use (ever, type, years exposure), alcohol use (ever, exposure [drinks/week], years exposure)
- 8.2.4 Comorbid conditions: Hepatitis B and C co-infection, cardiovascular disease (y/n, type), psychiatric conditions (y/n, type), non-cancer pulmonary conditions (y/n, type), hepatic dysfunction, hematologic abnormalities, renal dysfunction, neurologic disorders, endocrine disorders (including thyroid disorders, and diabetes)
- 8.2.5 HIV care: Current ART regimen, years of ART use, year of HIV diagnosis, history of opportunistic infections, most recent HIV viral load and CD4+T-cell count relative to participant visit).

8.2.6 Status of cancer diagnosis (one of the following):

- New diagnosis, pre-treatment phase
- New diagnosis, treatment phase
- Prior diagnosis, in remission (within 5 years of initial diagnosis or treatment)
- Prior diagnosis, recurrent, pre-treatment phase
- Prior diagnosis, recurrent, treatment phase
- Prior diagnosis, recurrent, no treatment planned

8.2.7 For participants with a new diagnosis (pre-treatment or treatment), the following will be collected:

- Cancer type, date of cancer diagnosis, method of diagnosis (clinical, cytology, histology), type of pathology performed (Hematoxylin and Eosin, immunohistochemistry, other), date of pathology, staging, staging methods (clinical, radiographic, surgical), date(s) of staging, current ECOG Performance Status (PS), current laboratory values (this would include complete blood count, renal and liver function, electrolytes)
- Cancer treatment plan: Detailed planned or current treatment. This should encompass surgical interventions, radiotherapy, and chemotherapy (agent names), including dates of planned or current therapy, and whether cancer care is being received or will occur at the enrolling institution.

8.2.8 For participants with a prior diagnosis in remission, the following will be collected:

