- Cancer history: Cancer type, date of diagnosis, prior method of diagnosis (cytology, histology), pathology performed, date of pathology, staging, staging methods (clinical, radiographic, surgical), current ECOG PS. Records from a prior diagnosis/treatment should be requested, but if they are unavailable, participant report will be sufficient.
- Current method of post-treatment surveillance (clinical, laboratory, radiographic), and current schedule of follow-up with this center.
- Prior cancer treatment. This should encompass surgical interventions, radiotherapy, and chemotherapy. Records from a prior diagnosis/treatment should be requested, but if they are unavailable, participant report will be sufficient.

8.2.9 For participants with a prior diagnosis, recurrent (pre-treatment, treatment, or no planned treatment) the following will be collected:

- Initial cancer type, date of diagnosis
- Cancer history: prior method of diagnosis (cytology, histology), pathology performed, date of pathology, staging, staging methods (clinical, radiographic, surgical), date(s) of staging. Records from a prior diagnosis/treatment should be requested, but if they are unavailable, participant report will be sufficient.

- Prior cancer treatment. This should encompass surgical interventions, radiotherapy, and chemotherapy. Records from a prior diagnosis/treatment should be requested, but if they are unavailable, participant report will be sufficient.
- Current date of cancer diagnosis, method of diagnosis (clinical, cytology, histology), pathology performed, date of pathology, staging, staging methods (clinical, radiographic, surgical), date(s) of staging, current ECOG Performance Status (PS), current laboratory values (this would include complete blood count, renal and liver function, electrolytes).
- IF THERAPY IS PLANNED OR UNDERWAY: Detailed planned or current treatment. This should encompass surgical interventions, radiotherapy, and chemotherapy, dates of planned or current therapy, and whether cancer care is being received or will occur at the enrolling institution.
- IF NO THERAPY IS PLANNED: Reason for no further therapy, e.g., if the decision for no therapy is based on lack of options for treatment, lack of benefit of further treatment, or participant choice not to pursue further treatment.

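### Section 3.1.3 makes active, non-advanced cancer with no treatment under consideration ineligible, although the enrollment form and Table 9-A provide for such cases when the disease is recurrent

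*Combined protocol and SAP*

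**What the plan says.** **Entry rule.** Section 3.1.3 first asks for cancer diagnosed or treated in the last 5 years, then states: "Participants will qualify under one of three categories".

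- Category 1, new, primary or recurrent: "Considering or currently receiving cancer treatment".
- Category 2, metastatic or locally advanced: "This includes cases for which there are no current definitive therapy options for cure (i.e., inoperable) but may be considered for non-standard / non-curative therapies".
- Category 3, prior diagnosis in remission: "Not currently on cancer treatment other than ART or maintenance therapy".

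Section 3.2 makes anyone who does not meet Section 3.1 ineligible. Section 3.0 adds that "no exceptions to eligibility criteria will be granted under any circumstance" and lets sites use the section as a signed eligibility checklist.

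**Later sections.**

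- Section 8.2.6 offers the status "Prior diagnosis, recurrent, no treatment planned", with no restriction to advanced disease.
- Section 8.2.9 asks why no therapy is planned. One listed reason is "participant choice not to pursue further treatment".
- Table 9-A counts recurrent cases with no anti-cancer therapy planned. It introduces advanced, inoperable disease with the word *including*, so that is one reason among others. (The row is labelled as prior cases, but its definition describes recurrent disease.)
- Table 2-A, in Section 2.2, lists "best supportive care/watchful waiting" among the planned-treatment options.

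**The concern.** The entry rule and the data model disagree about who belongs in the study. Read literally, Section 3.1.3 turns away someone whose non-advanced recurrence is untreated by choice, while Sections 8.2.6 and 8.2.9 hold a code and a question for that person. Read loosely, a site enrolls someone who fails the signed checklist.

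Two results are at stake. Section 10.1.2 estimates new and existing cases per month, and Table 9-A splits cases by disease class. Section 10.3 estimates the proportion of trial-eligible people who enroll on AMC trials and compares those who did with those who did not. Someone who has declined treatment may well decline a trial too, and Section 2.1 singles out people who opt out of trials as especially informative. Losing part of that group through the entry rule is a selection effect that cannot be repaired afterwards.

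**Working it through.** **1. The plan's own figures.** Table 10-A uses p ± [1.96 × √(p(1−p)/n) + 1/(2n)]. For hematologic malignancies, p = 0.273:

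- n = 360: 1.96 × 0.0235 + 0.0014 = 0.047, giving 22.6% to 32.0%, as printed.
- n = 720: 1.96 × 0.0166 + 0.0007 = 0.033, giving 24.0% to 30.6%, as printed.

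All eight intervals reproduce to 0.1 point. The gap does not touch this arithmetic. It affects who is counted.

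**2. Who fits a category.**

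| Situation | Section 3.1.3 | Sections 8.2.6, 8.2.9 and Table 9-A |
|---|---|---|
| Undecided about treatment | Category 1 | Depends on the plan made |
| Untreated, metastatic or locally advanced | Category 2 | Recurrent: provided for. New: no untreated class |
| In remission | Category 3 | Provided for |
| Recurrent, active, not advanced, no treatment considered | None | Provided for |
| New, active, not advanced, no treatment considered | None | No class; only Table 2-A hints at it |

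The fourth row is a direct contradiction. The fifth is a gap that runs through the entry rule, the status list (new diagnoses have only pre-treatment and treatment phases) and the primary-case row of Table 9-A (only planned or ongoing first-line therapy).

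**3. What the screening list can recover.** Under Section 8.1 it holds age, sex at birth, race/ethnicity and cancer type for everyone presenting with histologically confirmed cancer. Section 12.1 rules out further data on people who do not consent. The list therefore supports a count by cancer type. It has no disease or treatment status, so it cannot separate new from existing cases or fill the Table 9-A classes. It also lacks the stage, characteristics and quality-of-life data needed for Section 10.3.

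**4. Size, by illustration.** The documents give no share u of presenting cases in the gap. Assume 2%, 5% or 10%, with everyone eligible consenting. Reaching N enrolled then leaves out N × u/(1−u) people:

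| u | N = 360 | N = 720 |
|---|---|---|
| 2% | 7 | 15 |
| 5% | 19 | 38 |
| 10% | 40 | 80 |

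**5. Effect on the secondary proportion.** Suppose a share u of trial-eligible people falls in the gap and none of them enrolls on a trial. The observed proportion is then the true one divided by (1−u). With u = 10% (assumed), a true 27% reads 0.27/0.90 = 30%, and a true 4.5% reads 5.0%. The relative overstatement is 1/0.90 = 1.11. The absolute error depends on the enrollment rate, which is also unknown.

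**The case against.** The strongest reply is that the gap is narrow and the conflict mostly reconcilable.

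- Most untreated people still qualify: advanced disease under category 2, remission under category 3, and anyone undecided under category 1. This stands. A reader might infer that untreated patients as a whole drop out of the burden estimate. The documents do not support that, and the screening list also keeps the cancer type of those in the gap who have histological confirmation.
- The no-treatment status and the listed reasons could all be used for advanced recurrent cases. They could, but neither Section 8.2.6 nor Section 8.2.9 limits them so, and the word *including* in Table 9-A points the other way.
- Watchful waiting is listed as a kind of planned treatment, so such a patient may arguably meet category 1. This stands as an ambiguity. It does not help a person who has declined treatment or was not offered it.
- A reader might infer that refusal of therapy will look rare. People enrolled while considering therapy who then do not start are recorded at week 12, and Section 2.2 includes patient preference among the reasons. Only those who had already decided before being approached are missed.
- A reader might apply an assumed share to the 763 annual cases in Table 10-B. That total is all cancers the sites report seeing. It is not limited to active disease or to people who would enroll, so the result would not be a count of people lost to the study.
- Section 10.3 also requires an indication for the trial intervention, so some people in the gap would not be in the secondary denominator. This stands and limits the bias.

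**Conclusion.** The concern holds for one group: people with active cancer that is neither metastatic nor locally advanced, for whom no treatment is being considered. For recurrent disease, Section 3.1.3 contradicts Sections 8.2.6 and 8.2.9 and Table 9-A. For new diagnoses the entry rule, the status list and the primary-case row all lack a place for them, and only Table 2-A suggests that they were expected.

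The loss falls on the new and existing counts, the Table 9-A classes and the secondary comparison. Cancer-type counts taken from the screening list are unaffected for histologically confirmed cases. The enrolled proportion is overstated only if people in the gap meet the minimal trial criteria and rarely enroll.

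The size cannot be derived from the documents. The 7 to 40 people at N = 360 and 15 to 80 at N = 720 rest on an assumed share of 2% to 10% and full consent. The case for acting rests on the textual contradiction and the low cost of removing it.

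**What to change.** 1. Reword category 1 of Section 3.1.3 along these lines: *new, primary or recurrent diagnosis with active disease, whether or not treatment is planned or being received*.
2. Add to Section 8.2.6 a status *new diagnosis, no treatment planned*, and let Section 8.2.7 cover it, reusing the reason question already in Section 8.2.9.
3. Align the Table 9-A case rows so that every eligible person falls in exactly one class. The labels and definitions of its recurrent and prior rows should be reconciled at the same time.

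The cost is one eligibility amendment and one code-list entry, with matching edits to Section 8.2.7 and Table 9-A. No follow-up visit is added: under Section 5.1 and Appendix I, people with no treatment planned have only the enrollment encounter. The change concerns study entry and classification, not anyone's clinical care.

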3.2 Exclusion Criteria

Participants who do not fulfill the criteria as listed in [Section 3.1](#) above are ineligible.

3.3 Number of Participants to be Enrolled

NIH policy requires that women and members of minority groups and their subpopulations be included in all NIH-supported biomedical and behavioral research projects involving NIH-defined clinical research unless a clear and compelling rationale and justification establishes to the satisfaction of the funding Institute & Center (IC) Director that inclusion is inappropriate with respect to the health of the participants or the purpose of the research.

3.3.1 Proposed sample size

This study will enroll a minimum of 360 participants and a maximum of 720 participants.

3.3.2 Accrual rate

Approximately 10-20 participants per month across domestic AMC sites.

4.0 REGISTRATION PROCEDURES

4.1 Investigator and Research Associate Registration with CTEP

This study is non-interventional and is therefore exempt from IND requirements. However, **the following registration policy must be followed in accordance with Cancer Therapy and Evaluation Program (CTEP) policy.**

Food and Drug Administration (FDA) regulations and National Cancer Institute (NCI) policy require all individuals contributing to NCI-sponsored trials to register and to renew their registration annually. To register, all individuals must obtain a CTEP Identity and Access Management (IAM) account at <https://ctepcore.nci.nih.gov/iam>. In addition, persons with a registration type of Investigator (IVR), Non-Physician Investigator (NPIVR), or Associate Plus (AP) (*i.e.*, clinical site staff requiring write access to Oncology Patient Enrollment Network (OPEN), Rave, or acting as a primary site contact) must complete their annual registration using CTEP's web-based Registration and Credential Repository (RCR) at <https://ctepcore.nci.nih.gov/rcr>.

RCR utilizes five registration types.

- IVR: MD, DO, or international equivalent,
- NPIVR: advanced practice providers (*e.g.*, NP or PA) or graduate level researchers (*e.g.*, PhD),
- AP: clinical site staff (*e.g.*, RN or CRA) with data entry access to CTSU applications (*e.g.*, Roster Update Management System [RUMS], OPEN, Rave),
- Associate (A): other clinical site staff involved in the conduct of NCI-sponsored trials, and
- Associate Basic (AB): individuals (*e.g.*, pharmaceutical company employees) with limited access to NCI-supported systems.

RCR requires the following registration documents:

Documentation Required	IVR	NPIVR	AP	A	AB
FDA Form 1572	✓	✓			
Financial Disclosure Form	✓	✓	✓		
NCI Biosketch (education, training, employment, license, and certification)	✓	✓	✓		
GCP training	✓	✓	✓		
Agent Shipment Form (if applicable)	✓				
CV (optional)	✓	✓	✓		

An active CTEP-IAM user account and appropriate RCR registration is required to access all CTEP and Cancer Trials Support Unit (CTSUS) websites and applications. In addition, IVRs and NPIVRs must list all clinical practice sites and Institutional Review Boards (IRBs) covering their practice sites on the FDA Form 1572 in RCR to allow the following:

- Addition to a site roster,
- Assign the credit or consenting (IVR only) tasks in OPEN,

- Act as the site-protocol Principal Investigator (PI) on the IRB approval, and
- Assign the Clinical Investigator (CI) role on the AMC Delegation of Tasks Log (DTL).

In addition, all investigators act as the Site-Protocol PI, consenting, or as the CI on the AMC DTL must be rostered at the enrolling site with a participating organization (*i.e.*, Alliance).

Additional information is located on the CTEP website at <https://ctep.cancer.gov/investigatorResources/default.htm>. For questions, please contact the **RCR Help Desk** by email at [contact].

4.2 Site Registration

All U.S. based sites must be members of the NCI Central Institutional Review Board (NCI CIRB). Sites participating with the NCI Central Institutional Review Board (NCI CIRB) must submit the Study Specific Worksheet for Local Context (SSW) to the CIRB using IRBManager to indicate their intent to open the study locally. The NCI CIRB's approval of the SSW is automatically communicated to the CTSU Regulatory Office, but sites are required to contact the CTSU Regulatory Office at [contact] or [contact] to establish site preferences for applying NCI CIRB approvals across their Signatory Network. Site preferences can be set at the network or protocol level. Questions about establishing site preferences can be addressed to the CTSU Regulatory Office by emailing the email address above or calling [name], or by contacting the AMC ODMC (see protocol roster).

In addition, the Site-Protocol PI (*i.e.*, the investigator on the IRB approval) must meet the following five criteria to complete processing of the IRB approval record:

- Holds an active CTEP registration status,
- and on the AMC site roster,
- If using NCI CIRB, rostered on the NCI CIRB Signatory record,
- Includes the IRB number of the IRB providing approval in the Form FDA 1572 in the RCR profile, and
- Holds the appropriate CTEP registration type for the protocol.

Additional Requirements

Additional requirements to obtain an approved site registration status include:

- An active Federal wide Assurance (FWA) number,
- An active roster affiliation with the Lead Protocol Organization (LPO) or a Participating Organization, and
- Compliance with all protocol-specific requirements (PSRs).

